Changes from baseline in facial lesion counts will be analyzed separately by type (inflammatory and non-inflammatory) using an ANCOVA (Analysis of Covariance) model including baseline count, analysis center, and treatment as factors. The primary analysis will be performed using the ITT population using the primary imputation method for missing values.

The p-value for the treatment comparison, estimate of the LSMEANS treatment difference (CD5789 50 µg/g – Vehicle), and the 95% confidence interval of the LSMEANS difference will be generated from the ANCOVA model.

The treatment-by-analysis centers and the treatment-by-baseline lesion counts interactions for Change in Lesions Counts will be assessed separately by the interaction term at Week 12 at alpha level of 0.10. The consistency of the treatment effect across analysis centers will be evaluated using descriptive statistics and using graphical methods. The consistency of the treatment effect by baseline lesion counts will be evaluated using graphical methods.

In addition, change in Lesions Counts will be summarized descriptively at each visit.

Sensitivity analyses

The above primary efficacy analysis will be repeated using the PP population using the primary multiple imputation method for missing values.

To assess the robustness of the primary efficacy result, the following sensitivity analyses will be conducted for each of the 3 co-primary efficacy endpoints (see Section 4.1) using the ITT population:

- a. The same imputation method above will be repeated based on the Pattern-Mixture Model⁽²⁾ under the missing not at random (MNAR) assumption, by using the profiles from vehicle subjects with observed data to impute missing data.
- b. LOCF (Last observation carry forward) approach
- c. Subjects with missing IGA data at Week 12 will be considered as ‘failures’ for IGA success rate; and subjects with missing lesion counts data at Week 12 will be assigned the median change of lesion count data from subjects who are ‘failures’ of IGA success within the same treatment group.

7.4.1.2 *Analysis of the Secondary Efficacy Endpoint*

The same statistical methods planned for the 3 co-primary efficacy endpoints will be used for the analyses of the 3 co-secondary efficacy endpoints using the ITTT population, with Multiple Imputation (MI) as primary imputation method for missing values (see Section 7.4.2.2).

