7.4.2.1 Adjustment for covariates

The analysis of change from baseline in lesion counts will use an adjustment for the number of baseline lesions as described in Section 7.4.1.1.

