The ITTT population is potentially a subset of the ITT population with moderate truncal acne at the Baseline visit. In practice, this excludes from the ITT population the children between 9 and 11 years old who did not meet inclusion criterion #4 (PGA) or #5 (Truncal lesion counts) at study entry (i.e. who do not have PGA of 3, at least 20 inflammatory lesions on the trunk and at least 20 non-inflammatory lesions on the trunk).

The PP/PPT Population will be determined prior to breaking the study blind using the criteria described in Section 5.5.

7.4.2.7 *Active-Control studies intended to show equivalence*

Not applicable.

7.4.2.8 *Examination of Subgroups*

All subgroup analyses are exploratory in nature.

To determine whether the treatment effect is consistent across various subgroups, the estimate of the between-treatment effect (with a nominal 95% CI) for the primary efficacy endpoint will be estimated and plotted within each category of the following classification variables:

- Age Group [<18 years (“9-11 years”, “12-14 years”, “15-17 years”), ≥18 years (“18-64 years”, “≥65 years”)]
- Gender (female, male)
- Race (white, non-white)
- Country (US, Canada)
- Skin Phototype (I-III, IV-VI)

Treatment effects and nominal 95% confidence intervals by category for the classification variables listed above will be reported as well as presented graphically. Formal statistical testing of these interactions will not be performed.

For success rate on IGA, treatment effects and the nominal 95% confidence intervals will be summarized by category for the subgroup variable using the same method as the primary analysis.

For the change in lesion counts by type, treatment effects and the nominal 95% confidence intervals will be summarized by category for the subgroup variable using two-sample t-test.

7.5 **Safety analysis**

All safety analyses are descriptive, and no formal inferential testing will be performed.

7.5.1 **Extent of exposure**

7.5.1.1 *Study Duration*

Study duration (day) is defined as the date of the last visit minus the date of the Baseline visit plus one. Study duration will be summarized by descriptive statistics using the ITT population.

7.5.1.2 *Treatment Duration*

Treatment duration (day) is defined as “the date of the last application on face or the trunk, whichever is later, minus the date of the first application on face or the trunk, whichever is earlier, plus one”.

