2.5. Subpopulations

Three subpopulations of the ITT population will be studied using the primary and secondary efficacy analyses. Those populations are defined as:

- Subjects with at least 75% non-inflammatory baseline lesions. A subject's baseline total non-inflammatory lesion count will be divided by their baseline total lesion count (inflammatory and non-inflammatory). If the result is greater than or equal to 0.75, they will be included in the subpopulation. Presence of nodules and/or cysts will not be included for the calculation of inflammatory lesion counts.
- Subjects with no prior use of topical or oral retinoids. Use of topical and oral retinoids are identified using the ATC4 codes of D10AD and D10BA from the concomitant medication dataset.
- Subjects with no prior use of medications for acne. Subjects with use of prior medication of acne are identified using the following indication terms from the concomitant medications dataset:
 - ACNE
 - ACNÉ
 - ACNE ULGARIS
 - ACNE CONGLOBATA
 - ACNE FACE WASH
 - ACNE FACE/CHEST/BACK
 - ACNE ON FACE
 - ACNE VULARIS
 - ACNE VULGARIS
 - ACNE VULGARIS AND PITYROSPORUM FOLLICULITIS
 - ACNE VULGARIS OF FACE
 - ACNE VUOLGARIS
 - ACNE WASH
 - AKNE VULGARIS
 - FACIAL ACNE
 - FACIAL ACNE VULGARIS

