6.2. Multiple Imputation – Missing at Random

A multiple imputation method will be used to account for missing data on efficacy analyses. The following steps will be followed:

- 1) For lesion counts, the pattern of missingness in the data will be evaluated. If the data is not monotone missing, the MCMC method will be used to make it monotone missing. The single chain method will be used, with 200 burn-in iterations and 100 iterations between imputations. Fifty imputations will be created. The seed number will be 18251. Lesion counts generated as a result of the MCMC method will be re-imputed if they are below zero; they will not be rounded.
- 2) The MI procedure in SAS will be used to create multiple imputations of the data that have no missing values. If the MCMC method was previously employed, one imputation will be made using each of the fifty MCMC-imputed datasets. If the MCMC method was not used, fifty imputations will be created using the MI procedure assuming the data is Missing at Random. The seed number will be 18251. These imputations will use the following models:
 - a. For IGA and PGA scores, a logistic regression model will be used with covariates for treatment and non-missing data from earlier scheduled time points including baseline. Weeks will be imputed sequentially, with IGA/PGA data at prior non-baseline weeks treated as continuous data (baseline will be treated as categorical).
 - b. For lesion counts, a linear regression model will be used with covariates for treatment and non-missing data from earlier scheduled time points including baseline.
- 3) The imputed datasets will be analyzed as follows:
 - a. For IGA and PGA scores, the number of successes at Week 12 will be analyzed using the CMH test stratified by analysis center. The sample difference in proportions and its standard error will also be calculated. No continuity corrections will be used.
 - b. For lesion counts, change from baseline to Week 12 in lesion counts will be analyzed using an ANCOVA model with covariates for baseline count, analysis center, and treatment.
- 4) The resulting analysis on the imputed datasets will then be combined to produce a single set of statistics.

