6.8. Efficacy Subgroup Analysis

The subgroup analyses will repeat the analysis of the three co-primary and co-secondary endpoints on all subgroups. The MAR multiple imputation method will be used to handle missing data.

For lesion count subgroup analysis, the t-tests will be done assuming unequal variances using Satterthwaite's formula for variance.

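### Optional gain in precision, not an error: lesion-count subgroup effects use an unadjusted t-test although the plan otherwise adjusts this endpoint for baseline count

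*SAP*

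**What the plan says.** SAP 7.4.2.8 covers subgroup effects on the primary endpoint. For lesion-count change, "treatment effects and the nominal 95% confidence intervals will be summarized by category for the subgroup variable using two-sample t-test". In the same section, IGA success by subgroup keeps the primary method. The section also states that "All subgroup analyses are exploratory in nature" and plans no interaction test.

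Addendum 6.8 extends the subgroup work to the co-secondary endpoints and confirms the choice: "For lesion count subgroup analysis, the t-tests will be done assuming unequal variances using Satterthwaite's formula for variance". On missing values: "The MAR multiple imputation method will be used to handle missing data".

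Elsewhere, between-arm comparisons of this endpoint are adjusted for baseline:

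- SAP 7.4.1.1 uses an "ANCOVA (Analysis of Covariance) model including baseline count, analysis center, and treatment as factors".
- SAP 7.4.2.1 says that the analysis of change "will use an adjustment for the number of baseline lesions as described in Section 7.4.1.1".
- Addendum 6.2 has each imputed dataset "analyzed using an ANCOVA model with covariates for baseline count, analysis center, and treatment".
- Addendum 2.5 says "Three subpopulations of the ITT population will be studied using the primary and secondary efficacy analyses". On its natural reading, lesion counts in those subsets are also analyzed by ANCOVA.

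Neither document says why the subgroup levels are treated differently.

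**The concern.** With no interaction test, consistency across subgroups is judged from the estimates and nominal intervals alone. The overall estimate is adjusted and the subgroup estimates are not, so the two can differ because of the model as well as the subgroup. Chance imbalance in baseline count tends to be larger in small cells. The t-test leaves it in the estimate, while ANCOVA removes its linear part.

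At stake is the width of exploratory intervals. The primary and secondary tests, the type I error and the sample size are not affected.

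**Working it through.** **The plan's own figures (SAP 6).** For success rates of 23% and 15%, 90% power and two-sided 0.05, with pooled variance and no continuity correction:

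n = [1.960 × √(2 × 0.19 × 0.81) + 1.282 × √(0.23 × 0.77 + 0.15 × 0.85)]² / 0.08², which rounds up to 504 per arm. Then 504 / 0.84 = 600.

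Lesion-count power at 504 per arm is 97.8% for effect 3, SD 12, and 99.7% for effect 6, SD 20. All stated figures reproduce.

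**Inputs.** SDs of change of 12 (inflammatory) and 20 (non-inflammatory), planned effects of 3 and 6 lesions, and 16% for drop-outs and non-evaluable subjects, all from SAP 6. Assumed, because the documents do not give them: the within-arm correlation r between baseline count and change (0 to 0.7), and n per arm in a subgroup level.

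**Is a non-zero r plausible?** Change is the Week 12 count minus baseline. So r = 0 requires the Week 12 count to rise one-for-one with baseline. If baseline and Week 12 variances are equal (an assumption), |r| = √((1 − ρ)/2), where ρ is the correlation between the two counts. For ρ = 0.3, 0.5, 0.7 and 0.9 this gives 0.59, 0.50, 0.39 and 0.22.

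**Half-width of the 95% CI, complete data.**

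- t-test: t(0.975; 2n − 2) × SD × √(2/n)
- ANCOVA: t(0.975; 2n − 3) × SD × √(1 − r²) × √(2/n) × √((2n − 3)/(2n − 4))

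In large cells the ratio is √(1 − r²) = 0.954, 0.866 or 0.714 at r = 0.3, 0.5 or 0.7.

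| n per arm | SD | t-test | ANCOVA r = 0.3 | r = 0.5 | r = 0.7 |
|---|---|---|---|---|---|
| 20 | 12 | 7.68 | 7.44 | 6.75 | 5.57 |
| 50 | 12 | 4.76 | 4.57 | 4.15 | 3.42 |
| 100 | 12 | 3.35 | 3.20 | 2.91 | 2.40 |
| 300 | 12 | 1.92 | 1.84 | 1.67 | 1.38 |
| 100 | 20 | 5.58 | 5.33 | 4.84 | 3.99 |

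In simulation at 20, 50 and 100 per arm (4,000 runs per setting, SD 12), coverage was 94.4–95.4% for the t-test and 94.2–95.3% for ANCOVA. Both are valid. A skewed, floor-truncated baseline left the width ratios unchanged at a given r.

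**With missing data.** Simulation with 16% of Week 12 counts missing completely at random, regression imputation on treatment and baseline, 50 imputations and Rubin's rules (600 replicates). Entries are half-widths at r = 0 / 0.3 / 0.5 / 0.7.

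| n per arm | SD | t-test | ANCOVA |
|---|---|---|---|
| 30 | 12 | 6.82 / 6.85 / 6.71 / 6.56 | 6.86 / 6.63 / 6.00 / 4.95 |
| 100 | 12 | 3.67 / 3.64 / 3.59 / 3.52 | 3.68 / 3.50 / 3.19 / 2.63 |
| 100 | 20 | 6.13 / 6.09 / 6.02 / 5.86 | 6.14 / 5.87 / 5.33 / 4.38 |

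At 100 per arm the gain is about 4%, 11% and 25%, with coverage of 93–96% for both methods. The second decimal, especially at 30 per arm, is within simulation noise.

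**Where the choice would change the reading.** The half-width equals the planned effect at n = 2 × (1.96 × SD / effect)² × (1 − r²) per arm (complete data, normal approximation):

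- Inflammatory: 2 × (1.96 × 12/3)² = 123 for the t-test; 112, 92 or 63 for ANCOVA at r = 0.3, 0.5 or 0.7.
- Non-inflammatory: 2 × (1.96 × 20/6)² = 85 for the t-test; 78, 64 or 44 for ANCOVA.

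**The case against.** The best case for leaving the plan alone has five parts.

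- **No defect.** The Addendum revisited the method and kept it, so this is a reaffirmed choice for an exploratory analysis. That stands, and it is why this is only an option.
- **The useful range is narrow and may be empty.** Against 600 per arm, adjustment brings the inflammatory half-width below the planned effect only for levels holding 18.6–20.5% of subjects (r = 0.3), 15.4–20.5% (r = 0.5) or 10.4–20.5% (r = 0.7). For non-inflammatory counts the ranges are 12.9–14.2%, 10.7–14.2% and 7.3–14.2%. No planned level is shown to fall there. This stands as a limit. The entry criteria also restrict baseline, which makes r harder to guess.
- **Unequal variances.** The Addendum asks for them, and a model-based ANCOVA SE does not provide them. With a robust HC3 SE at r = 0.3, the width relative to the t-test is 1.07, 1.00, 0.99 and 0.96 at 10, 20, 30 and 100 per arm, so the gain is gone in small cells. At r = 0.5 it is 0.97, 0.91, 0.90 and 0.88, so a gain remains.
- **The missing-data check is simpler than the plan's imputation**, which also uses earlier visits. Adding one earlier visit (assumed correlation 0.8 with the outcome) lowers the t-test half-width at 100 per arm to about 3.42–3.44, with gains of 4%, 12% and 27%. The absolute widths move; the relative gain hardly does.
- **Workload and match.** Addendum 2.4 lists 17 levels across six variables. With four lesion endpoints that is 68 estimates, each reported twice if both methods are kept. Without center, the subgroup model still differs from the overall one.

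Sparse analysis centers within subgroups may explain the t-test. That argues against the center term, not against baseline count.

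**Conclusion.** The point holds as an optional, low-priority improvement. Subgroup effects on lesion-count change are the exception to a plan that otherwise compares arms on this endpoint with adjustment for baseline. The t-test is not wrong; it is less precise whenever baseline count predicts change to a useful degree.

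The gain rests on an assumed r: about 4–25% narrower intervals at 100 per arm with 16% missing data, for r between 0.3 and 0.7. The benefit lies mainly in mid-sized levels. At 30 per arm every inflammatory interval examined, under either method, has a half-width above the planned effect of 3, so very small levels stay uninformative.

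**What to change.** In SAP 7.4.2.8 and Addendum 6.8, before unblinding:

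- Within each subgroup level, estimate the treatment difference in lesion-count change by ANCOVA with treatment and baseline lesion count.
- Fit it on the 50 MAR-imputed datasets, combine with MIANALYZE, and report the LS mean difference with its nominal 95% CI.
- Leave out analysis center because cells are small, and say so. The aim is precision, not an identical model to SAP 7.4.1.1.
- Use one method for all levels of a variable on a plot, and keep the Satterthwaite t-test as a supplementary table.
- If a minimum level size is wanted, state it in advance. Use the t-test for every level of a variable when any level falls below it.
- Optionally, use an HC3 SE to keep the allowance for unequal variances.

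If the t-test is kept as the main method, one sentence giving the reason would be enough.

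**Cost.** Wording, one model statement, one degree of freedom per level and the extra table; baseline count is already collected. If r is near zero, the intervals are wider than the t-test's by:

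| n per arm | Model-based SE | HC3 SE |
|---|---|---|
| 10 | 2.6% | 11.7% |
| 20 | 1.2% | 5.3% |
| 30 | 0.9% | 3.5% |
| 100 | 0.2% | 1.0% |

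With the model-based SE, the break-even r is 0.22, 0.15, 0.13 and 0.06 at these sizes. With arms of 36 and 24 and an SD ratio of 1.3, in either direction, model-based coverage is 93.7–96.1%, against 95.4–95.6% with HC3.

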7.5.3 Cutaneous safety

Only local tolerability (erythema, scaling, dryness, stinging/burning) worsened from baseline will be analyzed.

Analyses of the local tolerability on the face will be based on the SAF population; and the analyses of the local tolerability on the trunk will be based on the SAFT population.

Number and percent of subjects with worsened local tolerability from baseline will be presented for each treatment group by the severity scale for each of the assessments (erythema, scaling, dryness, stinging/burning) by visit.

Number and percent of subjects with worst local tolerability worsened from baseline during treatment period will also be presented for each treatment group by the severity scale for each of the assessments (erythema, scaling, dryness, stinging/burning). The same will be presented for the final local tolerability worsened from baseline during the treatment period.

Summary statistics by treating the severity scale as continuous outcome will also be presented.

Subgroup analyses by Age Group (<18 years, ≥18 years), Race (white, non-white), Gender (female, male) and Skin Phototype (I-III, IV-VI) will be provided.

7.5.4 Laboratory parameters

A summary table of the categorical grade shift changes using the normal ranges from baseline to Week 12/ET will be presented for each treatment group by each laboratory category parameter using the SAF population.

Only subjects with both baseline and Week 12/ET assessments will be included in this analysis.

7.6 Other analyses

For the other variables, only observed data will be summarized without imputation for missing data. These data will be analyzed using the same methodology as described in Section 7.4.1.3.

7.6.1.1 Dermatology Life Quality Index (DLQI) / Children's Dermatology Life Quality Index(CDLQI)

DLQI(designed for use in adults, i.e. subjects over the age 16 years old) and C-DLQI (designed for use in children, i.e. subjects from age 5 to age 16) will be summarized descriptively.

Only SAF subjects who have both baseline and Week 12/ET assessments using the same age-appropriate questionnaire at both visits will be included in the analyses.

Total Scores and Change from Baseline at Week 12/ET for DLQI/C-DLQI, DLQI only, and C-DLQI only will be summarized.

In addition, number and percent of subjects will be reported by treatment group for each of the following categories of the effect of disease on the quality of life as specified in Table 2:

Table 2 DLQI/C-DLQI Categories			
DLQI		C-DLQI	
DLQI Category	Range of Total Score	C-DLQI Category	Score Maximum
No effect	0 - 1	No effect	0 - 1
Small effect	2 - 5	Small effect	2 - 6
Moderate effect	6 - 10	Moderate effect	7 - 12
Very large effect	11 - 20	Very large effect	13 - 18
Extremely large effect	21 - 30	Extremely large effect	19 - 30

Summaries of DLQI only and C-DLQI only by each dimension as defined in Table 3 below will also be provided.

Table 3 DLQI/C-DLQI Dimensions			
DLQI		C-DLQI	
DLQI dimensions	Score Maximum	C-DLQI dimensions	Score Maximum
Total Score	30	Total Score	30
Symptoms and feelings	6	Symptoms and feelings	6
Daily Activities	6	Sleep	3
Leisure	6	Leisure	9
Work and School	3	School or holidays	3
Personal relationships	6	Personal relationships	6
Treatment	3	Treatment	3

7.6.1.2 *Skin Oiliness Scale Questionnaire (SOS)*

SOS questionnaire will be summarized at baseline and Week 12/ET for SAF subjects. Number and percent of subjects choosing each answer will be reported by treatment group for each of the questions.

7.7 Analysis visit definition

All efficacy variables and local tolerability variables will be summarized and analyzed by analysis visit. Analysis visit will be imputed according to the following algorithm to summarize the data by proper visit window interval. Study day is calculated as visit date minus the date of first application plus 1.

Table 4 Analysis Visit and Visit Window			
Analysis Visit	Analysis Visit Number in Derived Dataset	Target Study Day	Visit Window (Study Day)
Baseline	1	1	[<= 1]
Week 1	2	8	[2 – 11]
Week 2	3	15	[12 – 21]
Week 4	4	29	[22 – 42]
Week 8	5	57	[43 – 70]
Week 12	6	85	>70

If multiple measurements are taken in the same interval, the one closest to the target study day will be used for the analysis. If two measurements are taken with equal differences in timing compared with the target date, the nominal visit number (recorded on the CRF page) will be used.

8 CHANGES FROM THE PROTOCOL ANALYSIS PLAN

Any change from the protocol will be justified and fully documented.

9 TABLE SHELLS AND REPORTING OUTPUT (GENERAL FEATURES)

The final list of tables and figures and their shells for the reporting of this study will be available in a separate document to be developed and will be finalized before database lock.

Details of analysis specifications including but not limited to the SAS code will be documented on the table shells.

2.1. Decimal Precision

Unless otherwise noted, means and medians will be presented to one more decimal place than the source data; standard deviations will be presented to two more decimal places than the source data; minimums and maximums will be presented to the same number of decimal places as the source data, percentages will be presented to one decimal place; confidence intervals will be presented to two decimal places; and p-values will be presented to three decimal places.

2.2. Missing Date Procedures

Adverse events with completely missing dates will be considered treatment-emergent. Medications with completely missing end dates will be considered concomitant. Adverse events and medications with partially missing start or end dates will be considered treatment-emergent and concomitant respectively unless the non-missing portion of the dates definitively proves otherwise.

For example, if a subject starts treatment on 10FEB2015, then adverse events with onset dates of FEB2015, 2015, or 05DEC would all be considered treatment-emergent, while onsets dates of 2014 or JAN2015 would not be considered treatment-emergent. Medications starting or ending in FEB2015 or 2015 would be considered concomitant, medications ending in JAN2015 or 2014 would not.

